Automated DOT (a-DOT), a smartphone app that uses facial recognition software and advanced features to detect noningestion, combines the accuracy of in-person DOT with the convenience of real-time centralized data collection and monitoring. Adding a daily side effect diary to a-DOT will further allow precise tracking of timing of both medication ingestion and side effects which may be compromising adherence. Zepatier (elbasvir and grazoprevir) is a new once-daily fixe-dose combination tablet which has achieved high rates of SVR ranging from 94 to 97 percent in genotype-1 infected patients including those with HIV/HCV coinfection and renal impairment. Zepatier is administered for 12 to 16 weeks, depending on HCV genotype, prior treatment history, and the presence of certain baseline NS5A polymorphisms (1a only). By administering Zepatier via this innovative a-DOT platform, we hypothesize that PWIDs treated in real-wrold settings can be successfully treated with high rates of adherence and SVR.

In this proposed 18-month trials, 75 PWIDs enrolled in opiate agonist treatment (genotypes 1a and 1b) with chronic HCV will be enrolled over a 12-month period, and randomized to either aDOT or treatment as usual (TAU). **We will recruit PWIDs from diverse community settings include a syringe exchange program (NYHRE), federally-qualified health center (Comprehensive Health Care Center), homeless shelter (The Living Room), and a methadone maintenance treatment program (Montefiore Wellness Centers).** All patients (including treatment-experienced and HIVV/HCV coinfectd subjects) will be treated with Zepatier-based regimens as per the standard of care. Rigorous data are necessary to judge the contribution of a-DOT to the success of HCV treatment in PWIDs. By performing a randomized trial of a-DOT HCV therapy (Zepatier with and without ribavirin), we will evaluate the efficacy of a-DOT for improving HCV treatment outcomes among PWIDs.

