- 1. To determine in a randomized trial whether HCV treatment delivered via a-DOT (Zepatier with and without ribavirin) provided on-site at community treatment programs during a 12-week study period is more efficacious than self-administered HCV treatment for enhancing adherence and SVR in PWIDs.** 75 subjects will receive Zepatier will be randomized to take medications by either treatment as usual (self-administration), automated directly observed therapy (a-DOT), or a-DOT with gamification (25 subjects in each arm). Those in the a-DOT arm will be observed taking their Zepatier dose by the smart-phone based interface. We hypothesize that adherence and SVR will be higher in a-DOT versus TAU subjects, and that SVR in a-DOT arm will be equivalent to SVR seen in registration trials.
- 2. To evaluate the feasibility and acceptability of a-DOT to both participants and HCV providers in tracking longitudinal patterns of adherence and providing adherence feedback in real-time.** We hypothesize that a-DOT will be highly acceptable to both participants and medical providers.
- 3. To determine whether gaming features added to the aDOT platform enhance adherence compared to standard aDOT.** For the 25 subjects randomized to the aDOT + gamification arm, subjects will compete with other subjects within this arm for modest cash incentives. Those with highest levels of adherence measured at monthly research visits compared to their peers will earn additional incentives.

4. To determine the impact of ongoing drug use (cocaine, opiates, or benzodiazepenes) and on HCV virologic outcomes in subjects receiving Zepatier by aDOT. We hypothesize that ongoing drug use during HCV treatment will not be associated with adherence in subjects randomized to a-DOT.

B. APPROACH

B.1. Preliminary Studies

B.1.1. Overview of the research team. [name] has focused on defining optimal models of HCV care for PWIDs over the last 15 years, and is expert in treating HCV in PWIDs, methadone and buprenorphine-maintained patients, and active drug users.

Monitoring and improving adherence to antiviral therapy in real world settings requires methods that address varied challenges in treating high-risk populations. While accuracy is paramount, cost, ease of deployment, desirability, scalability, privacy, and flexibility are also important for ensuring wide-scale utility.

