In our previous DOT study, mean adherence in the mDOT group was 87% (SD=12%, n=21), and mean adherence in the TAU group was 77% (SD=20%, n=19) which translates into a standardized effect size or Cohen's d = 0.6. Based on this effect size, the power of the mixed effects linear model for the repeatedly measured continuous adherence outcome will be greater than 80%, even if anticipated ICC is as high as 0.5.

We will determine the proportion (and Wald or exact 95% CI) of subjects randomized to aDOT arm (n=50) who achieve SVR. For example, if SVR is achieved in 70% of the 50 study participants, the 95% confidence interval around that proportion will be: 57%, 83%. If SVR is achieved in 80%, the 95% confidence interval will be: 69%, 91%. If SVR is achieved in 90%, the 95% confidence interval will be: 82%, 98%. The overall SVR for all subjects will be compared to historical controls to demonstrate feasibility of treating real-world injection PWIDs with Zepatier-based regimens. Although our study lacks power to definitively answer the question of whether a-DOT improves SVR, our study will provide an estimated effect size to be used in future R01-funded studies examining the efficacy of a-DOT.

We used power calculations for Fisher's exact test (with 80% power and 5% significance level in a two-tailed test) to find the minimum detectable difference between the percentage of "adherent" subjects in the favorable group (e.g. not actively using drugs) vs. unfavorable group (e.g. actively using drugs). We would be able to find that a characteristic is significantly associated with adherence if there are 71% "adherent" subjects in the favorable group vs. no more than 41% "adherent" subjects in the unfavorable group (3.55 in terms of odds ratio). When using adherence as a continuous measure, we will have greater power to show correlations between continuous predictor variables and adherence. We calculated the minimum detectable correlation coefficient with 80% power and 5% significance level to be 0.33 which represents a small to medium correlation effect size. Therefore, we expect to have sufficient power to detect some associations that are likely to exist.

We will determine an effect size with respect to the outcome of adherence in the aDOT + gamification arm vs. a-DOT arm which will inform future R01 interventions.

C. References

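### The SVR interval may be Wald or exact with no rule for choosing; all worked examples are Wald, which undercovers and passes 100% at n=50 and SVR of 94–97%

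*Combined protocol and SAP*

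**What the plan says.** Section B.10 (Analytic plan) defines the SVR estimate for the two a-DOT arms pooled (25 + 25): "We will determine the proportion (and Wald or exact 95% CI) of subjects randomized to aDOT arm (n=50) who achieve SVR". It does not say when the Wald or the exact interval will be used. Three illustrations follow:

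- "if SVR is achieved in 70% of the 50 study participants, the 95% confidence interval around that proportion will be: 57%, 83" (per cent)
- "If SVR is achieved in 80%, the 95% confidence interval will be: 69%, 91" (per cent)
- "If SVR is achieved in 90%, the 95% confidence interval will be: 82%, 98" (per cent)

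No illustration is given above 90%. The introduction, however, describes the drug as having achieved "high rates of SVR ranging from 94 to 97 percent in genotype-1 infected patients", and aim 1 hypothesises that "SVR in a-DOT arm will be equivalent to SVR seen in registration trials". Read together, these put the hoped-for a-DOT SVR in the mid-90s.

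**The concern.** The Wald interval takes its standard error from the observed proportion. As that proportion nears 1 the standard error shrinks towards zero, so in a small sample the interval is too short, is symmetric where it should be skewed, and can pass 100%. An SVR in the mid-90s with 50 subjects is such a case.

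Two things are at stake. First, B.10 concedes that the trial cannot settle whether a-DOT improves SVR, so the a-DOT proportion and its interval are a main SVR result. A lower limit that is too high makes the result look more secure than it is. Second, with two methods allowed and no rule, the choice can be made after the data are seen, between intervals whose lower limits differ by several points.

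**Working it through.** **Inputs.** n = 50 and a two-sided 95% level (B.10); example rates of 70%, 80% and 90% (B.10); reference SVR of 94–97% (introduction, joined with the aim 1 hypothesis).

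**Formulas.** With p = x/n and z = 1.96:

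- Wald: p ± z·√(p(1−p)/n).
- Exact (Clopper–Pearson): lower limit is the 2.5% quantile of Beta(x, n−x+1); upper limit is the 97.5% quantile of Beta(x+1, n−x).
- Wilson: [p + z²/2n ± z·√(p(1−p)/n + z²/4n²)] / (1 + z²/n).
- Coverage at true rate π: the sum of Binomial(50, π) probabilities over every x whose interval contains π.

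**Step 1: reproduce the plan's examples.** For 90%, 1.96·√(0.9·0.1/50) = 0.083, which gives 81.7–98.3%.

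| Responders | Plan | Wald | Exact | Wilson |
|---|---|---|---|---|
| 35/50 (70%) | 57–83 | 57.3–82.7 | 55.4–82.1 | 56.3–80.9 |
| 40/50 (80%) | 69–91 | 68.9–91.1 | 66.3–90.0 | 67.0–88.8 |
| 45/50 (90%) | 82–98 | 81.7–98.3 | 78.2–96.7 | 78.6–95.7 |

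All three stated intervals are Wald and none is exact.

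**Step 2: the same methods near the reference rates.**

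| Responders | Wald | Exact | Wilson |
|---|---|---|---|
| 47/50 (94%) | 87.4–100.6 | 83.5–98.7 | 83.8–97.9 |
| 48/50 (96%) | 90.6–101.4 | 86.3–99.5 | 86.5–98.9 |
| 49/50 (98%) | 94.1–101.9 | 89.4–99.9 | 89.5–99.7 |
| 50/50 (100%) | 100–100 | 92.9–100 | 92.9–100 |

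**Step 3: actual coverage of the nominal 95% interval.**

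| True SVR | Wald | Exact | Wilson |
|---|---|---|---|
| 90% | 87.9% | 97.0% | 97.0% |
| 94% | 80.7% | 99.1% | 97.1% |
| 95% | 92.0% | 98.8% | 96.2% |
| 96% | 86.7% | 98.6% | 95.1% |
| 97% | 78.1% | 98.3% | 93.7% |

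On a grid from 94% to 97% in steps of 0.01 points, Wald coverage runs from 78.1% to 94.9% (mean 88.0%), exact from 97.5% to 99.4%, and Wilson from 92.8% to 97.9% (mean 96.1%).

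**Step 4: direction of the misses.** At a true SVR of 94%, the Wald lower limit lies above the truth when x is 49 or 50. That has probability 0.1447 + 0.0453 = 0.190, against a nominal 0.025. All misses together are 1 − 0.807 = 0.193, so nearly every miss is flattering. At 97%, the zero-width interval at 50/50 alone accounts for 0.97⁵⁰ = 0.218 of the total miss probability of 0.219.

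**Step 5: how often the interval is visibly unusable.** The Wald upper limit passes 100% when x is 47, 48 or 49. That has probability 60.2% at a true SVR of 94% and 71.9% at 97%. Adding 50/50 (4.5% and 21.8%) gives 64.7% and 93.7%.

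**The case against.** The plan permits Wald but does not require it. An exact interval is already allowed, and B.10 pairs approximate with exact or rank methods elsewhere (chi-square with Fisher, t with Wilcoxon), so a reader could take the wording to mean exact where the approximation fails. That reading is fair to the intent, but no such rule is written for SVR. The 90% example is still Wald, although it implies only 50 × 0.10 = 5 failures.

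The 94–97% expectation is a join of the introduction and aim 1, not a stated planning value for this interval. Over true rates of 70–90%, the span of the plan's examples, mean Wald coverage is 92.9%, a mild shortfall. This stands as a limit on the severe figures. Coverage is nevertheless already 87.9% at 90%, a rate the plan itself illustrates.

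Coverage also moves in a sawtooth. It is 79.9% at a true rate of 94.11% and 94.9% at 94.12%, so the values at single rates should be read with the 88.0% mean. Wilson too dips below nominal in places.

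Finally, no margin or test depends on the limit, the planned historical comparison is of overall SVR in all subjects, and the study is described as a pilot (B.9.5). At 47/50 and 48/50 all three methods contain the whole 94–97% range. That lowers the consequence, but the reading does change at other counts. At 45/50 Wald includes 97% and exact (upper limit 96.7%) does not. At 49/50 Wald excludes 94% (lower limit 94.1%) and exact does not.

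**Conclusion.** The concern holds. The method for the a-DOT SVR interval is left open, the only method illustrated is Wald, and Wald is unsuitable at the response rates the trial hopes to see. If true SVR lies between 94% and 97% and all 50 a-DOT subjects are in the denominator, nominal 95% Wald coverage averages 88.0%, falls to 78.1%, and does not reach 95% at any rate on the grid. Almost all of the error lies in lower limits that are too high.

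The lower limit differs between Wald and exact by 4.0 points at 47/50 (87.42 − 83.45) and 4.3 points at 48/50 (90.57 − 86.29). If SVR turns out nearer 70–80% the shortfall is small. The plan's examples are arithmetically correct as Wald intervals. The point is confined to the SVR estimate and does not touch the adherence analyses, the power statements or the sample size.

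**What to change.** In B.10, delete the Wald option and name one method in advance for every SVR proportion. Either Clopper–Pearson or Wilson will serve, but the plan should commit to one. Clopper–Pearson is the smaller edit, since the plan already allows an exact interval, and its coverage does not fall below 95%. Wilson is shorter on average, with mean coverage close to nominal.

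Recompute the illustrations with the chosen method. For 70%, 80% and 90% these are 55–82%, 66–90% and 78–97% by Clopper–Pearson, or 56–81%, 67–89% and 79–96% by Wilson. Add one example in the reference range, such as 48/50: 86.3–99.5% by Clopper–Pearson or 86.5–98.9% by Wilson.

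The cost is a wording change, with no extra subjects or data. Reported lower limits at high SVR will be about four to five points less favourable than Wald would show at 47 to 49 responders, and about seven points lower at 50/50.

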B.9.6. Subject Compensation. Subjects will receive \$25 for each research visit and \$10 for each returned blister pack. Subjects randomized to the a-DOT arm (n=50) will receive additional incentives based on adherence measured at monthly visits: \$10 for 50% adherence; \$20 for 80% adherence; and \$30 for 95% adherence. For the subjects further randomized to the a-DOT + gamification intervention, the second-most adherent participant will receive an additional \$35 incentive, while the top-most adherent patient will receive a \$50 incentive at their subsequent study visit. Should the top two participants be tied, the participant with the most adherent time of dosing will be awarded the first-place prize. In total, participants may earn up to \$453, including metrocards and incentives.

B.9.7. Data Management/Confidentiality. Data will be stored with study ID codes in locked filing cabinets, separate from name-based files, which will be stored in a different locked cabinet. All study information and name-based information will be kept in separate, password protected, HIPAA compliant REDCap databases online. All name-based information will be destroyed at the end of the study, while study-ID-based information will be deleted if participants decline to allow storage of their records for future research of 50 years. All participants will be informed of the data management and confidentiality plan at the time of consent to participate.

B.10. Analytic plan.

First, the success of randomization will be checked by comparing the a-DOT and TAU groups on key variables, such as age, gender, race, HCV viral load, advanced liver disease, psychiatric, and active drug use. Continuous variables will be compared between study arms using the Student's t or Wilcoxon test, and

categorical variables will be compared using chi-square or Fisher's exact tests. Variables that are not equally distributed will be included in multivariate models if they are also associated with the study outcome.

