Adherence to Zepatier (continuous measure) will be determined as the amount of medication taken by each patient during the first 12 weeks will be expressed as a percentage (with a 0-100% range) of the target dose. Subjects will be classified as "adherent" if they receive at least 80% of the total dose of Zepatier. Subjects who receive less than 80% of the total dose of Zepatier will be classified as "non-adherent." Analyses using self-reported adherence will also be conducted. Self-report is more accessible to clinicians than pill count, and there is added value in performing analogous analyses using the self-report measure.

Because adherence will be measured two ways (pill counts and self-report) *concordance correlation coefficients* will be calculated and performed to evaluate agreement between the measures. We will also test if the means of the two measurements are equal. Because adherence will be measured monthly, mixed-effects linear models for repeated measures that account for within-subject correlation will be used. In addition, we will examine the adherence data using a dichotomous cut-off (adherence \geq 80%), and determine the proportion of subjects who were sometimes, always, or never adherent during the 12-week treatment period. To this end, separate analyses will be performed for pill count and self-report adherence data.

For subjects randomized to the a-DOT arm, association between active drug use during treatment and the continuous adherence will be tested using Student's t or Wilcoxon signed rank test, depending on normality of the data. Bivariate analysis of dichotomous adherence data with categorical variables will be performed with chi-square and Fisher exact tests. We will conduct multivariate logistic regression analyses based on findings from the univariate analysis, but recognize that our modest sample size will limit such models.

Based on our pilot data, if we conservatively assume that 80% of subjects in the a-DOT will achieve \geq 80% adherence (v. 50% in the TAU arm), we will have $>$ 80% power to find a statistically significant difference. With the application of mixed-effects logistic regression to the repeatedly measured binary adherence outcome, power will be greater than 80% no matter how large the within-subject outcome correlation or intraclass correlation (ICC).

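### The stated 80% power to detect 71% vs 41% adherent is not reached with 75 or with 50 subjects, and the drug-use comparison names a paired Wilcoxon test for independent groups

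*Combined protocol and SAP*

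**What the plan says.** All of this is in section B.10 (Analytic plan) of the combined protocol and SAP unless another place is named.

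- **Power statement.** The calculation is for Fisher's exact test, "with 80% power and 5% significance level in a two-tailed test". It compares a "favorable group (e.g. not actively using drugs) vs. unfavorable group (e.g. actively using drugs"). The result is that an association would be found "if there are 71% 'adherent' subjects in the favorable group vs. no more than 41% 'adherent' subjects in the unfavorable group", also given as an odds ratio of 3.55. No N and no split are stated. A minimum detectable correlation of 0.33 follows, also without an N.
- **Assumed adherence by arm.** The arm comparison is powered "if we conservatively assume that 80% of subjects in the a-DOT will achieve" the 80% adherence threshold, against 50% in TAU.
- **Drug-use analysis.** "For subjects randomized to the a-DOT arm, association between active drug use during treatment and the continuous adherence will be tested" with Student's t or the "Wilcoxon signed rank test, depending on normality of the data". The next sentence reads: "Bivariate analysis of dichotomous adherence data with categorical variables will be performed with chi-square and Fisher exact tests".
- **Numbers of subjects.** B.2 randomizes 25 to each of three arms, 75 in all. B.9.6 confirms the a-DOT total: "Subjects randomized to the a-DOT arm (n=50) will receive additional incentives".
- **Aim 4** hypothesises that ongoing drug use is not associated with adherence among subjects randomized to a-DOT.

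**The concern.** The test, level, sidedness and both rates are given, so the claim can be checked for any N and split. A 30-point difference near the middle of the scale normally needs more than 40 per group for 80% power, and this trial has 75 subjects in total. The plan's own example, drug use, is an aim confined to 50 of them.

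The direction of Aim 4 makes this matter. When the hypothesis is no association, the stated power is what would make a non-significant result look informative. An overstated figure lends such a result more weight than the data can carry.

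Separately, the signed rank test needs paired values. Users and non-users are different people, and the plan describes no within-subject comparison of periods with and without use.

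**Working it through.** **Inputs.** From B.10: p1 = 0.71, p2 = 0.41, two-sided alpha 0.05, Fisher's exact test. From B.2, B.9.6 and B.10: N = 75 or N = 50. The split is not stated, so all splits with at least 5 per group were tried. Splits are written favorable/unfavorable. No attrition is assumed.

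**Odds ratio.** (0.71/0.29)/(0.41/0.59) = 3.52, which agrees with 3.55 within rounding of the rates.

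**Power.** Sum Bin(x; n1, p1) × Bin(y; n2, p2) over all tables (x, y) that the test rejects. Fisher rejects when its two-sided p-value is at most 0.05. The uncorrected chi-square rejects when |x/n1 − y/n2| / √[p̄(1−p̄)(1/n1+1/n2)] ≥ 1.96.

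| N | Split | Fisher | Chi-square |
|---|---|---|---|
| 75 | 37/38 | 71.0% | 78.3% |
| 75 | 38/37 | 71.9% | 79.2% (maximum) |
| 75 | 39/36 | 72.6% (maximum) | 74.5% |
| 50 | 25/25 | 50.6% | 62.3% |
| 50 | 26/24 | 52.2% | 63.6% (maximum) |
| 50 | 28/22 | 54.6% (maximum) | 58.2% |
| 50 | 35/15 | 45.3% | 51.5% |
| 50 | 15/35 | 40.4% | 51.3% |

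At N = 75, Fisher power is 70% to 73% for splits from 34/41 to 41/34. The 35/15 split applies the 30% on-treatment drug use reported in B.1.3 to 50 subjects. The 15/35 split is its mirror, shown because Table 1 requires illicit drug use in the past six months.

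**Attempts to reproduce 80%.** With 75 subjects, the most favourable rounding of the rates (71.5% vs 40.5%) gives Fisher at most 75.6%. The pooled normal approximation gives 75.5%, and a one-sided 5% Fisher test 78.5%. Equal groups need 48 each (80.1%; 47 each gives 78.7%), or 96 subjects.

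**Shortfall.** N = 75, Fisher: 80 − 73 = 7 to 80 − 70 = 10 points. N = 50: 80 − 54.6 = 25.4 points or more with Fisher, and 80 − 63.6 = 16.4 or more with chi-square.

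**Base rate.** Overall adherence implied by 71%/41% is (n1 × 0.71 + n2 × 0.41)/N: 62% at 35/15, 56% at 25/25, 50% at 15/35. B.10 assumes 80% in a-DOT, and across the trial (50 × 0.80 + 25 × 0.50)/75 = 70%. The effect of aligning the rates depends on what is held fixed.

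- *N = 50, 80% overall, odds ratio 3.55 fixed.* Fisher power: 25/25 (89.5% vs 70.5%) 27%; 35/15 (86.6% vs 64.6%) 39%; 15/35 (91.5% vs 75.1%) 16%.
- *N = 50, 80% overall, 30-point difference fixed*, with p2 = 0.80 − 0.30 × n1/50. Fisher power: 25/25 (95% vs 65%) 70%; 28/22 (93.2% vs 63.2%) 73%; 35/15 (89% vs 59%) 63%. At 15/35 the favorable rate would be 101%, which is impossible. These are values at named splits, not bounds.
- *N = 75, 70% overall, 30-point difference fixed.* Fisher power at 38/37 (84.8% vs 54.8%): 81%.

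**Correlation.** Detectable r = tanh[2.802/√(n−3)]: 0.32 at n = 75, 0.39 at n = 50. A value of 0.33 corresponds to n of about 70.

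**Precision for Aim 4.** The 95% half-width for a difference in mean adherence is 2.011 × SD × √(1/n1 + 1/n2), with 48 df and the two SDs quoted in B.10. SD 12%: 6.8 points (25/25) to 7.4 (35/15). SD 20%: 11.4 to 12.4.

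**The case against.** **The 50-subject reading is an inference.** This stands. The power sentence concerns any characteristic, with drug use as an example. The explicit a-DOT restriction in B.10 is attached to continuous adherence, and the sentence on dichotomous adherence does not repeat it. The correlation of 0.33 fits about 70 subjects. A reader might infer that the plan claimed 80% power for 50 subjects, but the documents do not say so. The literal claim fails on either N.

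**Chi-square is also listed.** With 75 subjects near an even split it closes most of the gap. But the plan says its calculation was for Fisher, and with 50 subjects chi-square still stops at 64%.

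**The base-rate mismatch need not hurt the plan.** This stands too. A reader might infer from the 16% to 39% figures that the drug-use analysis is nearly powerless. Those figures hold the odds ratio fixed, whereas the plan describes its target as a difference in percentages and gives the odds ratio in parentheses. With a 30-point difference held fixed, power is 63% to 73% at the three N = 50 splits shown, and about 81% at 38/37 with all 75.

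**Nothing says a null result will be taken as proof.** Correct. B.9.5 calls the study a pilot, and B.10 claims power only for some associations and admits that its modest sample limits multivariate models. The risk lies in how Aim 4 is framed, not in a stated decision rule.

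**Signed rank is a slip.** Probably so: it is paired with Student's t, and the opening of B.10 says only Wilcoxon for group comparisons. It still needs correcting.

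**Conclusion.** The power statement is wrong as written. For 71% vs 41% with two-tailed Fisher at 5%, this design gives at most 73% with 75 subjects and at most 55% with 50. The likeliest error is 7 to 10 points, if all 75 were meant. Carrying the 80% over to the a-DOT drug-use analysis overstates power by about 25 points or more with Fisher, or about 16 or more with chi-square. The maxima cover every split with at least 5 per group, and the 7-to-10-point range assumes a near-even split. Both take full follow-up.

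The rates are inconsistent with the adherence B.10 assumes elsewhere, but the documents do not settle whether aligning them would lower or raise power. That depends on N, the split and the scale held fixed.

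The signed rank test does not fit two independent groups. The whole point concerns secondary analyses. It does not show that the trial is too small for its arm comparison.

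**What to change.** In B.10:

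1. Beside the power statement, give the N, the assumed split and the base rate. Restate the power or minimum detectable difference for each analysis it serves, including the 50-subject a-DOT drug-use analysis. Say whether a difference or an odds ratio is held fixed, and reconcile the base rate with the assumed 80% and 50%. As illustrations only, keeping 71% in the favorable group, 80% Fisher power needs about 37% in the other group at 37/38 (odds ratio 4.2) and about 30% at 25/25 (odds ratio 5.7).
2. State the N behind the correlation of 0.33.
3. Replace the signed rank test with the Wilcoxon rank-sum test.
4. For Aim 4, report the user vs non-user adherence difference with its 95% confidence interval, and do not read a non-significant test as support for no association. With 50 subjects, expect a half-width of about 7 points at SD 12% and 11 to 12 points at SD 20%.

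The cost is wording in one section and one interval from data already being collected. The stated detectable effect will look less favourable for the literal rates. Sample size and the arm comparison do not change.
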